## **Remote Ischemic Preconditioning Study / Renal Transplant**

**PI: [name]**

**Co-Investigators:**

### **Specific aim:**

[figure not shown]
Remote ischemic preconditioning (RIPC), a phenotype of ischemic preconditioning, has been found to provide protection from I/R in humans. Several proof of concept clinical trials have shown that transient ischemia reperfusion of lower extremities confers protection to kidneys in patients undergoing endovascular or open surgical repair of an abdominal aortic aneurysm and in patients undergoing cardiac surgery. Furthermore, a randomized pilot clinical trial demonstrated that application of RIPC in high risk patients with kidney dysfunction undergoing coronary angioplasty reduced the incidence of procedure related contrast media induced AKI. To date the efficacy of RIPC in protecting renal allografts from I/R injury during renal transplantation has not been systematically investigated. **In this current proof of concept proposal we will test the central hypothesis that application of RIPC in donors and recipients during live donor kidney transplantation will reduce the severity of graft injury and improve outcome. We propose the following specific aim: To examine the effect of RIPC on clinical and biochemical markers of graft function in patients undergoing live donor kidney transplantation.**

In this study, patients undergoing live donor kidney transplantation will be allocated to the control group or RIPC group. Before allograft implantation, RIPC will be accomplished both in the donor and the recipient by inducing intermittent extremity ischemia through four five cycles of oscillometric blood pressure cuff inflation. The monitored clinical end points will include total urine output following kidney reperfusion over three days, plasma creatinine declination over five days, initiation of dialysis, and development of graft injury. Magnitude of graft injury will be measured using biochemical markers, such as, plasma and urinary concentration of neutrophil gelatinase associated lipocalin (NGAL), IL-18, and KIM-1. By rejecting our null hypothesis, RIPC may serve as a safe, cost-effective protective strategy to prevent allograft injury in the clinical setting of live donor kidney transplantation.

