#### **4.3 Outcomes**

The degree of allograft injury will be assessed by the levels of urinary biomarkers NGAL, IL-18, and KIM-

1. The primary endpoints will be the level of graft function in the early post transplantation period categorized as follows: delayed graft function (DGF) (defined as the need for dialysis within the first week of transplantation), slow graft function (SGF) (defined as <40% decrease in serum creatinine by POD 3), and immediate graft function (IGF) (defined as >40% reduction in serum creatinine by POD3). Incidence of allograft primary malfunction will be based on urine output during the first three days after

transplantation, the one month serum creatinine concentration, one month estimated GFR calculated according to diet modification. Additional secondary endpoints include 90 day mortality, length of ICU stay, and length of hospital stay.

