#### **4.4 Statistical Analysis**

The sample size calculation is based on a projected difference of NGAL levels between the two study arms. Hall et al reported a mean NGAL level of 49 mg/mL (SD = 37 mg/mL) for a group of patients that had immediate graft function and a mean NGAL level of 248 mg/mL in a group of patients with slow graft function. (which Hall reference is this) Based on these data we consider a conservative estimate of a mean difference between study groups to be 35 mg/mL NGAL. Using these assumptions, an alpha level of 0.05 and 80% power, we calculate a sample size of n= 19 per study group. Variables such as biomarkers, blood pressure, creatinine, and urine output that are expressed at multiple time points will be compared between the groups using repeated measures of ANOVA. Categorical variables will be expressed as percentages and will be compared using chi-squared analysis. A  $p$  value  $<0.05$  will be considered to be a statistically significant difference.

Ref#1 Perico(2004) delayed graft function in kidney transplantation Lancet 364(9447): 1814-1827 Perico, N., et al. (2004). "Delayed graft function in kidney transplantation." Lancet **364**(9447): 1814-1827

Ref #2 (old ref #11)

Ref#3 Rabb,H(2012) The promise of immune cell therapy for acute kidney injury.journal of clinical investigation122(11):3852-54(old ref #38)

Ref#4 Perico P (2004) Delayed graft function in kidney transplantation Lancet 364(9447):1814-1827

Ref#5 Siedlecki a etal(2011) Delayed graft function in kidney transplant Am j Transplant 11 (11) :2279-2296(old ref#42)

Ref#6 (OLD REF#6)

i Perico, N., et al. (2004). "Delayed graft function in kidney transplantation." *Lancet* **364**(9447): 1814-1827

ii Eltzschig ,H k and T.Eckle (2011). Ischemia and reperfusion –from mechanisms to translation *Nature Medicine* **17**(11) :1391-1401

iii Rabb,H(2012). The promise of immune cell therapy for acute kidney injury.*journal of clinical investigation***122**(11):3852-54

iv same as #1. Perico, N., et al. (2004). "Delayed graft function in kidney transplantation." *Lancet* **364**(9447): 1814-1827

v Siedlecki a etal. (2011). Delayed Graft Function in Kidney Transplant. *Am j Transplant* **11** (11) :2279-2296

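### The graft-function classes in 4.3 have no dialysis exclusion, precedence or boundary rule, and 4.4 would analyse creatinine lowered by dialysis as graft function

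*Combined protocol and SAP*

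**What the plan says.** Section 4.3 of the combined protocol and SAP introduces the primary endpoint with "The primary endpoints will be the level of graft function in the early post transplantation period categorized as follows". Three definitions follow:

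- The worst class rests on dialysis only: "delayed graft function (DGF) (defined as the need for dialysis within the first week of transplantation".
- The middle class rests on creatinine only: "slow graft function (SGF) (defined as <40% decrease in serum creatinine by POD 3".
- The best class likewise rests on creatinine only: "immediate graft function (IGF) (defined as >40% reduction in serum creatinine by POD3".

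The first has no creatinine condition. The other two have no dialysis condition, and neither names the baseline from which the fall is measured. Section 4.3 gives no order of precedence and no rule for creatinine measured after dialysis. Nothing elsewhere supplies one: 2.1 only repeats the dialysis definition of DGF, and the Specific aim lists starting dialysis and "plasma creatinine declination over five days" as separate end points.

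For the analysis, 4.4 states: "Categorical variables will be expressed as percentages and will be compared using chi-squared analysis". It sends creatinine, with the other variables measured at several times, to a repeated-measures ANOVA, again with no mention of dialysis.

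**The concern.** There are two linked problems.

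The first is classification. A chi-squared test on a three-level outcome needs each patient in exactly one level. As written, the levels are neither exclusive (DGF overlaps each of the other two) nor exhaustive (a fall of exactly 40% without dialysis has no level). For the few dialysed patients, the primary endpoint would depend on a choice the plan does not make.

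The second is measurement. Dialysis removes creatinine, so a fall after dialysis is not evidence that the graft is filtering. Nothing in 4.3 or 4.4 separates such values from the rest. If one arm has more dialysis, its creatinine curve is pulled down by the treatment of its worst grafts, and the comparison tends to favour that arm. If remote ischemic preconditioning reduced dialysis, that arm would be the control arm and the distortion would run towards no effect.

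**Working it through.** **Step 1. Apply the three definitions literally.**

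| Dialysed in first week | Creatinine fall by POD 3 | Classes met |
|---|---|---|
| Yes | 30% | DGF and SGF |
| Yes | exactly 40% | DGF only |
| Yes | 50% | DGF and IGF |
| No | 30% | SGF |
| No | exactly 40% | none |
| No | 50% | IGF |

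Every dialysed patient whose fall is not exactly 40% meets two classes. The DGF-and-IGF row has two routes: dialysis before POD 3 produces the fall, or the graft produces it and dialysis first becomes necessary on days 4 to 7. SGF and IGF do not overlap each other.

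**Step 2. The number of patients.** Section 4.4 gives 19 per group, from an NGAL difference of 35, an SD of 37 (units as printed), alpha 0.05 and 80% power. A two-sided two-sample t-test with these inputs needs 18.55 per group, rounded up to 19, with power 81.0%. The stated figure is reproduced. It rests on NGAL, so this point does not change it. The total is 2 × 19 = 38.

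**Step 3. Expected dialysed patients.** Section 2.1 gives DGF in 4-10% of live-donor transplants. Assume that rate across both arms and independent patients.

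- Expected number: 38 × 0.04 = 1.52; 38 × 0.10 = 3.8.
- Chance of at least one: 1 − 0.96^38 = 0.79; 1 − 0.90^38 = 0.98.
- Chance of at least two: 0.45 to 0.90 (binomial, same inputs).

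**Step 4. How many meet both DGF and IGF.** The documents do not give the share of dialysed patients with a fall above 40%. Assuming 25% to 100%, the range is 1.52 × 0.25 = 0.38 up to 3.8 × 1 = 3.8 patients.

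**Step 5. The creatinine series.** If dialysis lowers one patient's value at a given time by d, that arm's mean falls by d/19. If one arm has k more such patients than the other, the difference in means moves by k × d/19 in its favour. The documents give neither d nor the timing of dialysis relative to sampling, so the direction follows but the size does not.

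**The case against.** The strongest reply is that the ordinary reading is hierarchical. DGF is listed first, the three levels run from worst to best, the wording implies one level per patient, and 4.4 cites a study that treats immediate and slow function as separate groups. An analyst would probably assign every dialysed patient to DGF, and the 34 to 36 patients expected not to be dialysed are classed without ambiguity, apart from the trivial case of exactly 40%. Much of this stands: the gap is one of drafting and touches few patients. But the precedence is not written, and a primary endpoint should not depend on a convention left to the analyst. Reading DGF first also does nothing for the creatinine series.

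A reader might infer more than the documents support, in three ways:

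- **That the plan counts dialysed patients as successes.** It does not. It defines no success, every dialysed patient also meets DGF, and the text permits but does not direct placing such a patient in IGF.
- **That one reclassified patient would decide the trial.** Any comparison with so few events is fragile. That is a property of sparse data and does not measure the effect of the overlap. The DGF count depends on dialysis alone and changes only if someone overrides it.
- **That the creatinine comparison is seriously biased towards no effect.** The direction depends on which arm has more dialysis, and the size is unknown. Nor is the creatinine series the primary endpoint.

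**Conclusion.** The point holds in a limited form and should be corrected. As written, the primary endpoint places nearly every dialysed patient in two classes and leaves one boundary case in none, while the planned test needs exactly one class each. Separately, the repeated-measures ANOVA would treat dialysis-lowered creatinine as graft function, which tends to favour the arm with more dialysis.

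About 1.5 to 3.8 of 38 patients would be dialysed, with a 79-98% chance of at least one. This rests on the protocol's background rate applying to both arms and on full recruitment. The number who would meet both DGF and IGF, and the bias in the creatinine curves, cannot be fixed from the documents.

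**What to change.** **In 4.3.** Keep the plan's definition of DGF and state that it takes precedence whatever the creatinine. Define SGF as not DGF with a fall of 40% or less by POD 3, and IGF as not DGF with a fall of more than 40%. Measure both from a named pre-transplant creatinine, for example the last value before surgery.

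**In 4.4.** State that creatinine measured after post-transplant dialysis is not treated as graft function. Add one pre-specified rank comparison between arms of the POD 3 creatinine ratio (POD 3 value over the named baseline), with dialysed patients ranked worst. Setting post-dialysis values aside leaves gaps in the series for the worst grafts, so the text should say that the rank comparison is what accounts for those patients.

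Both changes should be fixed before outcomes are seen by arm. They are endpoint and analysis rules and do not touch patient management.

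**Cost.** A few sentences, no new data and no change to the sample size. The price is a little extra analysis and a rank result that is harder to interpret clinically than a difference in means.

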#### **4.4 Statistical Analysis**

The sample size calculation is based on a projected difference of NGAL levels between the two study arms. Hall et al reported a mean NGAL level of 49 mg/mL (SD = 37 mg/mL) for a group of patients that had immediate graft function and a mean NGAL level of 248 mg/mL in a group of patients with slow graft function. (which Hall reference is this) Based on these data we consider a conservative estimate of a mean difference between study groups to be 35 mg/mL NGAL. Using these assumptions, an alpha level of 0.05 and 80% power, we calculate a sample size of n= 19 per study group. Variables such as biomarkers, blood pressure, creatinine, and urine output that are expressed at multiple time points will be compared between the groups using repeated measures of ANOVA. Categorical variables will be expressed as percentages and will be compared using chi-squared analysis. A  $p$  value  $<0.05$  will be considered to be a statistically significant difference.

Ref#1 Perico(2004) delayed graft function in kidney transplantation Lancet 364(9447): 1814-1827 Perico, N., et al. (2004). "Delayed graft function in kidney transplantation." Lancet **364**(9447): 1814-1827

Ref #2 (old ref #11)

Ref#3 Rabb,H(2012) The promise of immune cell therapy for acute kidney injury.journal of clinical investigation122(11):3852-54(old ref #38)

Ref#4 Perico P (2004) Delayed graft function in kidney transplantation Lancet 364(9447):1814-1827

Ref#5 Siedlecki a etal(2011) Delayed graft function in kidney transplant Am j Transplant 11 (11) :2279-2296(old ref#42)

Ref#6 (OLD REF#6)

i Perico, N., et al. (2004). "Delayed graft function in kidney transplantation." *Lancet* **364**(9447): 1814-1827

ii Eltzschig ,H k and T.Eckle (2011). Ischemia and reperfusion –from mechanisms to translation *Nature Medicine* **17**(11) :1391-1401

iii Rabb,H(2012). The promise of immune cell therapy for acute kidney injury.*journal of clinical investigation***122**(11):3852-54

iv same as #1. Perico, N., et al. (2004). "Delayed graft function in kidney transplantation." *Lancet* **364**(9447): 1814-1827

v Siedlecki a etal. (2011). Delayed Graft Function in Kidney Transplant. *Am j Transplant* **11** (11) :2279-2296

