## **2.1 Background**

Kidney transplant is the ultimate treatment for end stage renal disease. It improves the quality of life and survival of the patient. Acute kidney injury (AKI) caused by ischemia reperfusion occurs to some extent in cadaveric renal allografts , invariably in the non-beating heart setting and in some live donor transplants leading to varying degrees of delayed graft function (DGF). DGF due to AKI is defined as the need for dialysis in the first week after transplantation and complicates 4-10% of live donor and 5-50% of cadaveric kidney transplants.i Several lines of experimental evidence suggest that ischemia reperfusion injury (I/R) plays a critical role in the pathogenesis of DGF. The kidney with its high adenosine triphosphate (ATP) consumption and complex vascular architecture is particularly vulnerable to I/R injury. A variety of therapeutic measures have been implemented to decrease the incidence of DGF.ii These measures include maintenance of normovolemia, avoidance of arterial hypotension, and avoidance of nephrotoxic drugs in the recipient. Minimizing cold and warm ischemia time have also been advocated to minimize graft injury; however, these measures have not significantly decreased the rate of occurrence of DGF after kidney transplantation.iii, iv Given the increasing demand for kidney allografts, new diagnostic and therapeutic measures are needed to reduce AKI and DGF following kidney transplant and to improve outcome.v, vi,

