### **4. Experimental Design**

This will be a randomized controlled trial to evaluate the influence of RIPC administered intraoperatively on the magnitude of allograft injury in patients undergoing live donor kidney transplantation. The study will be conducted after the institutional board approval and informed consent will be obtained from each patient (both the donor and the recipient). Patients undergoing live-donor kidney transplants >19 years of age will be enrolled in this study. Perioperative immunosuppressive agents will be administered according to the institution protocol, and all patients will undergo general endotracheal anesthesia.

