#### **4.2 Measurements**

For each patient, approximately ten milliliters of urine will be collected at zero, six, and twelve hours after transplantation, as well as, postoperative day one and two. Time zero will be defined as the time surgery is completed per documentation in the anesthesia flow sheet. Each sample will be placed in a centrifuge at 3300 RPM for three minutes. The urinary supernatant will be frozen at -80 Celsius and assayed in batches for NGAL and IL-18. Both urine NGAL and IL-18 will be quantified using ELISA testing. Serum and urine creatinine concentrations will be measured by the Jaffe assay using the P-module of a Cobas analyzer (Roche diagnostics, Indianapolis, IN) and the Beckman creatinine analyzer system (Beckman Instruments Inc., Fullerton CA).

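### The 80% power for NGAL in Section 4.4 uses an SD from immediate-function patients only, although the arms are not selected on graft function

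*Combined protocol and SAP*

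**What the plan says.** Section 4.4 sizes the trial on NGAL: "The sample size calculation is based on a projected difference of NGAL levels between the two study arms". It takes two published figures. The first is "a mean NGAL level of 49 mg/mL (SD = 37 mg/mL) for a group of patients that had immediate graft function". The second is "a mean NGAL level of 248 mg/mL in a group of patients with slow graft function", with no SD. It then states: "Based on these data we consider a conservative estimate of a mean difference between study groups to be 35 mg/mL NGAL". With alpha 0.05 and 80% power it arrives at 19 per group. Biomarkers measured repeatedly "will be compared between the groups using repeated measures of ANOVA".

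Three other places show who will be in the arms:

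- Section 4 (Experimental Design): "Patients undergoing live-donor kidney transplants >19 years of age will be enrolled in this study". Graft function is not an entry criterion, and it is known only after surgery.
- Section 4.3 (Outcomes) classifies recipients as having immediate (IGF), slow (SGF) or delayed (DGF) graft function, and makes that classification the primary endpoint.
- Section 2.1 (Background) says that DGF "complicates 4-10% of live donor and 5-50% of cadaveric kidney transplants".

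**The concern.** An SD of 37 describes the spread among recipients whose grafts worked at once. The calculation needs the spread across everyone in an arm, which also includes the distance between immediate- and slow-function patients. On the plan's own figures that distance is 248 − 49 = 199 units, more than five times the SD used.

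The 80% figure is the only justification given for 19 per group, and NGAL is a planned measure of graft injury. If the real chance of detecting 35 units is well below 80%, a non-significant NGAL result could be misread as evidence that RIPC does nothing. The point concerns the NGAL comparison only. It says nothing about power for the graft-function categories in Section 4.3.

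**Working it through.** **1. The plan's own figure.** Difference 35, SD 37, 1:1 allocation, two-sided alpha 0.05 (the plan does not state sidedness; two-sided reproduces its n). Standardised difference d = 35/37 = 0.946. The two-sample t-test needs n = 18.55, so 19 per arm, with power 81.0% at 19 and 78.7% at 18. The arithmetic is correct.

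**2. Slack.** With 19 per arm the t-test has 80% power at d = 0.934. The largest SD compatible with 35 units is therefore 35/0.934 ≈ 37.47.

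**3. SD of a mixed arm.** Let p be the share of non-immediate recipients, with mean 248 and SD s:

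SD² = (1 − p)·37² + p·s² + p(1 − p)·199²

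Even with s = 0, this exceeds 37² whenever p < 1 − 1369/39601 = 0.965. An SD above 37 therefore does not depend on the unknown s.

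**4. Power from the plan's own formula** (common SD, 19 per arm, difference 35). The documents give no SGF rate, no DGF mean and no SD for either group. I *assume* p of 4–10%, which joins the Section 2.1 DGF rate to the Section 4.4 SGF mean. I take s as 37 (same SD) or 187 (same coefficient of variation, 248 × 37/49). Smaller shares are shown for scale.

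| p | s | SD | Power | Difference detectable at 80% |
|---|---|---|---|---|
| 1% | 37 | 42.0 | 71% | |
| 2% | 37 | 46.3 | 62% | |
| 1 in 38 | 37 | 48.8 | 58% | |
| 4% | 37 | 53.8 | 50% | 50 |
| 4% | 187 | 65.1 | 37% | 61 |
| 10% | 37 | 70.2 | 32% | 66 |
| 10% | 187 | 91.1 | 21% | 85 |

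For example, p = 4% and s = 37 give SD² = 1369 + 0.04 × 0.96 × 39601 = 2890, so SD = 53.8. The chance of at least one such patient among 38 is 79% at p = 4% and 98% at p = 10%.

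**5. Dependence on the effect model.** A mixture is not normal, so power was also simulated (pooled t-test, one time point, normal and lognormal components). The first two models are sized to a mean difference of 35.

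| Effect model | s | p = 4% | p = 10% |
|---|---|---|---|
| Uniform 35-unit shift | 37 | 54–56% | 35% |
| Uniform 35-unit shift | 187 | 52–58% | 30–36% |
| Proportional reduction | 37 | 80–86% | 48% |
| Proportional reduction | 187 | 70–79% | 34–41% |

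The proportional reduction required is 35/(49 + 199p), which is 61% at p = 4% and 51% at p = 10%. At p = 5% its power is 74–78% with s = 37 and 61–72% with s = 187. With no non-immediate patients the two models give 81–82% and 97% or more, so in both of them power falls as the share rises.

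A third possibility is that RIPC acts only by preventing non-immediate function. A 35-unit difference then needs a drop of 35/199 = 17.6 percentage points. At p = 4–10% the most that could be gained is 199p = 8 to 20 units. Even with 17.6% in control and none in RIPC, power is 32–33% (s = 37) or 15–18% (s = 187).

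**6. The word *conservative*.** 35 units is 18% of the IGF–SGF gap (35/199) but 71% of the IGF mean (35/49). It is small against the first and large against the second, and the plan does not say which comparison it intends.

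**The case against.** The strongest reply is that every power figure below 80% needs an input the documents do not supply. The 4–10% is a DGF rate attached to an SGF mean, and the SD of non-immediate patients is unknown. This stands, and it is why the figures are a sensitivity range. It does not touch the mismatch itself, because step 3 holds with no spread at all among non-immediate patients.

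Second, the uniform shift, which gives low power throughout, is unrealistic: it puts 32–42% of treated concentrations below zero. A proportional effect is more plausible, and with s = 37 it roughly holds 80% at a 4% share. That also stands, though the lowest run there was 79.9%, and 80% is lost at 5%.

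Third, the test simulated is not the planned analysis. NGAL "urine will be collected at zero, six, and twelve hours after transplantation, as well as, postoperative day one and two", and averaging five samples gains precision. Under the shift formula with s = 37, correlations of 0.5 to 0.8 between samples give 71–57% power at p = 4% and 49–37% at p = 10%. Reaching 80% needs a correlation of at most 0.36 or 0.11 respectively. A log-scale test would help more: with a proportional effect and lognormal data, about 97% at p = 4% and 71–73% at p = 10%. Section 4.4 specifies no log scale, gives no correlation and claims neither gain, so neither supports the 80% as written.

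Finally, this is a proof-of-concept trial and NGAL is not among the primary endpoints in Section 4.3. That limits the consequence, but the plan still claims 80% power and rests its sample size on it.

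**Conclusion.** The concern holds. It is certain that an SD from immediate-function recipients was applied to arms not selected on graft function, and that 19 per arm leaves almost no room for a larger SD (37 used, about 37.47 allowed). The unqualified 80% is therefore unsupported.

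It is probable, not proved, that 80% is too high. With 4–10% non-immediate recipients at mean 248, one time point and a raw-scale test, simulated power runs from about 30% to 58% for a uniform shift and from about 34% to 86% for a proportional effect. An effect acting only through fewer non-immediate grafts could not produce 35 units at those shares. No single corrected power can be given, because the category mix, the SGF and DGF SDs, the effect model and the within-patient correlation are all unstated.

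**What to change.** Revise the sample-size paragraph in Section 4.4:

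- Replace 37 with an SD for all recipients that includes the spread between graft-function categories.
- State the assumed IGF/SGF/DGF mix, the category means and SDs, and the effect model (uniform, proportional or category shift). Mark each as sourced or assumed.
- For the existing 19 per group, give the power for 35 units, or the difference detectable with 80% power, as a range.
- Say whether the figure refers to one time point or to the five-sample comparison and, if the latter, with what assumed correlation.
- Justify the word *conservative* or remove it.

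Possible wording: *The SD of 37 applies to immediate-function recipients only. Assuming [share] non-immediate recipients (mean 248, SD [ ], assumed) and a [type] effect, the SD across all recipients is [ ]; with 19 per group the power to detect 35 is [ ]–[ ]%.*

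The cost is one paragraph and, probably, a less favourable power statement with some inputs openly marked as assumptions. Enrolment, endpoints and procedures do not change.

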
## 2.3 The role of biomarkers in assessment of Graft Injury/Acute Kidney Injury

Reliance on creatinine for the assessment of graft injury is inappropriate because creatinine is a measure of filtration function rather than true injury. Furthermore, serum creatinine is influenced by non-renal factors such as body weight, muscle mass, protein intake, and extracellular fluid volume. Secretion accounts for 10-40% of creatinine clearance, which could mask decreases in creatinine clearance. Most importantly, elevation in serum creatinine shows significant lag time after kidney injury.xxxiv

Multiple novel biomarkers are now available with potential to accurately diagnose graft injury in a timely fashion. There is evidence to suggest that biomarker expression precedes the clinical syndrome of renal failure. Therefore, by measuring kidney specific biomarkers we may identify graft injury before DGF develops.xxxv,xxxvi,xxxvii This may provide a unique opportunity for early intervention including aggressive resuscitation of patients with reversible renal hypoperfusion and early initiation of dialysis in patients with severe ATN based upon biomarker evidence. Indeed, the time delay between graft injury and loss of graft function resulting in serum creatinine elevation may explain the high morbidity and mortality associated with allograft failure. NGAL, IL-18, and KIM-1 have been measured in urine for early diagnosis of graft injury and as markers of graft recovery and function.xxxviii,xxxix, xl, xli, xlii

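### The serial creatinine comparison names no baseline adjustment, giving up precision that the reference value implied by the 40% rule could supply

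*Combined protocol and SAP*

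**What the plan says.** The specific aim lists among the clinical end points "plasma creatinine declination over five days". Section 4.3 classifies early graft function partly by the relative fall in creatinine, for example "slow graft function (SGF) (defined as <40% decrease in serum creatinine by POD 3", with immediate function on the other side of the same cut. Section 4.4 then gives one rule for all serial measurements: "Variables such as biomarkers, blood pressure, creatinine, and urine output that are expressed at multiple time points will be compared between the groups", using repeated-measures ANOVA.

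Three things are not stated. Section 4.4 names no baseline covariate, change score or baseline term, and does not say which time points enter the model or which term is tested. Section 4.3 does not say when the reference value for the 40% fall is taken. Section 4.2 gives collection times for urine but none for serum creatinine.

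**The concern.** Creatinine in the first days after transplantation starts from the recipient's pre-transplant level. The protocol itself says in section 2.3 that "serum creatinine is influenced by non-renal factors such as body weight, muscle mass, protein intake, and extracellular fluid volume". Several of these are lasting traits of the patient, so part of the spread between recipients after surgery was probably there before it. A model that ignores the starting value leaves that spread in the error term. With 19 per arm there is little information to spare, and the value that would remove the spread is already implied by the 40% rule. At stake is the precision of one named end point, the serial creatinine comparison.

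**Working it through.** **1. The plan's own figure.** Inputs from section 4.4: "an alpha level of 0.05 and 80% power"; a "conservative estimate of a mean difference between study groups to be 35 mg/mL NGAL"; "a mean NGAL level of 49 mg/mL (SD = 37 mg/mL"). Sidedness is not stated, so two-sided is assumed. By the normal formula, n = 2 × (1.960 + 0.842)² × (37/35)² = 17.5, so 18 per arm. By the noncentral t it is 19 per arm, with 81.0% power. This agrees with "we calculate a sample size of n= 19 per study group". The sizing arithmetic is sound, and it concerns NGAL, not creatinine.

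**2. What adjustment changes.** Under randomisation the two arms have the same expected pre-transplant creatinine. The expected arm difference in post-transplant level therefore equals, apart from sign, the expected arm difference in absolute fall. Adjustment leaves the target alone and reduces the variance.

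**3. Size of the gain.** The documents give no SD, effect or baseline correlation for creatinine. An effect of d = 0.65 SD is assumed, and r is shown over a range. Here r is the correlation between the reference value and the post-transplant quantity analysed.

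- Unadjusted: noncentrality = d × √(n/2) = 0.65 × √9.5 = 2.003; 36 df; critical value 2.028; power 49.6%.
- Adjusted: d is replaced by d/√(1 − r²); 35 df; critical value 2.030. The last column also multiplies the residual variance by 1 + 1/34, an approximate allowance for estimating the slope.

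| r | variance left, 1 − r² | adjusted d | noncentrality | power | power with slope allowance |
|---|---|---|---|---|---|
| 0 | 1.00 | 0.650 | 2.003 | 49.5% | 48% |
| 0.2 | 0.96 | 0.663 | 2.045 | 51.1% | 50% |
| 0.3 | 0.91 | 0.681 | 2.100 | 53.3% | 52% |
| 0.5 | 0.75 | 0.751 | 2.313 | 61.4% | 60% |
| 0.7 | 0.51 | 0.910 | 2.805 | 77.9% | 77% |

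For an assumed d of 0.80, with the slope allowance, unadjusted power of 67% becomes 67%, 70%, 78% and 91% at r = 0.2, 0.3, 0.5 and 0.7.

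**4. How the baseline should enter.** A simulation of 4,000 trials per setting assumed 19 per arm, five post-transplant values correlated 0.7 with each other, a shift of 0.80 SD, and a baseline correlated r with each value.

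| r with each value | post-transplant values only | baseline as a time point, group effect | change from baseline | baseline as covariate |
|---|---|---|---|---|
| 0.2 | 80% | 73% | 55% | 80% |
| 0.3 | 78% | 70% | 60% | 81% |
| 0.5 | 78% | 66% | 78% | 91% |
| 0.7 | 79% | 64% | 98% | 99.5% |

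Entering the baseline as an ordinary time point dilutes the group effect, because the arms cannot differ systematically there. Change scores lose power when r is low: for a single post-transplant value their variance is 2(1 − r), which exceeds 1 when r is below 0.5. The covariate model is at least as good as each alternative in every row.

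**The case against.** The strongest reply is that little depends on this. The sample size rests on NGAL, and the graft-function category already uses each recipient's own relative fall. The size of the gain depends on an r that the documents do not supply. All of that stands. The illustrations also leave out dialysis, which lowers creatinine directly; section 2.1 puts delayed graft function at 4–10% of live-donor transplants.

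Three stronger readings are tempting, and the documents do not support them.

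- A reader might infer that the plan estimates the level of creatinine and so misses the decline named in the aim. Under randomisation the two absolute contrasts have the same expectation (step 2). Nor is chance imbalance a separate harm. An imbalance of at least 0.3 SD in baseline would occur in about 36% of trials this size, but the unadjusted standard error already allows for it.
- A reader might take it as fact that raw levels will be compared. Section 4.4 is silent, and a group-by-time test that includes the pre-transplant value would use the baseline. That reading does not rescue power, however. In simulations of exponential decline (assumed start 7 mg/dL, SD 2–3, decline rate 0.6 against 0.8 per day), the sphericity-corrected group-by-time test had about 7–10% power. The unadjusted comparison had 21–38% and the covariate model 26–53%.
- A reader might take it as documented that a suitable pre-transplant value is collected. The 40% rule implies that some earlier value exists, but its timing and the serum schedule are undefined. The fix therefore has to define it.

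**Conclusion.** The point holds as one of precision and clarity. Section 4.4 specifies no baseline adjustment for serial creatinine, although section 4.3 needs an earlier value for each recipient. For an assumed 0.65 SD effect and 19 per arm, the power forgone is about 11 to 12 points at r = 0.5 and 28 points at r = 0.7 (27 with the slope allowance). It is about nil at r of 0.2 or below. In the worst case, r = 0, adjustment costs about one point. The direction is secure; the size is not, because r, the creatinine SD and the effect are all assumptions. There is no bias, and the sample size and the primary category stand as they are. It is a free improvement.

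**What to change.** In section 4.3, define the reference creatinine as the last pre-transplant value drawn before allocation is revealed, and state that the 40% rule uses this value. State the serum creatinine sampling times over the five days named in the specific aim.

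In section 4.4, state that the post-transplant creatinine values over those five days are analysed in the repeated-measures model with the reference value as a covariate and not as an outcome time point. The result to report is the baseline-adjusted difference between arms. Plain change scores should not be substituted.

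The cost is one degree of freedom and a few sentences. No extra patients are needed, and essentially no new data, since the 40% rule already requires a reference value; its availability before allocation is revealed should be confirmed when the definition is written.
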